6. To determine how AD skin endotypes and gene expression differ among the study outcome groups: (1) topical steroid responders, (2) dupilumab responders, (3) dupilumab non-responders, (4) non-AD, and (5) long-term dupilumab participants	8. Non-lesional and lesional skin tape endotypes determined in exploratory objective 4 9. Non-lesional and lesional skin biopsy endotypes determined in exploratory objective 4 (adults only) 10. Non-lesional and lesional skin tape transcriptome 11. Non-lesional and lesional skin biopsy transcriptome (adults only)	6. The clinical response to protocol's standard-of-care treatment among different AD participants will be associated with distinct AD skin endotypes and transcriptional profiles.
7. To determine skin gene expression changes that are associated with topical moisturizer treatment	12. Non-lesional and lesional skin tape transcriptome (long-term dupilumab participants excluded)	7. Clinical treatment with moisturizer is associated with changes in transcriptional profiles in the skin.
8. To determine skin gene expression changes that are associated with topical steroid response and non-response	13. Non-lesional and lesional skin tape transcriptome (non-AD and long-term dupilumab participants excluded)	8. Clinical response to topical steroids is associated with transcriptional profiles in the skin.
9. To determine skin gene expression changes that are associated with dupilumab response and non-response	14. Non-lesional and lesional skin tape transcriptome (dupilumab-naïve participants only) 15. Non-lesional and lesional skin biopsy transcriptome (adults only, dupilumab-naïve participants only)	9. Clinical response to dupilumab is associated with transcriptional profiles in the skin.
10. To determine the changes in cell type-specific gene and protein expression and cellular composition that are associated with dupilumab response and non-response	16. Single cell non-lesional and lesional skin biopsy transcriptome and proteome (dupilumab-naïve adults only)	10. Shifts in the cellular composition of skin and cell type-specific gene and protein expression changes underlie clinical response to dupilumab.
11. To determine whether AD skin endotypes are associated with topical steroid response	17. Non-lesional and lesional skin tape endotypes determined in exploratory objective 4	11. The clinical response to topical steroid treatment will be

Exploratory Objectives:	Related Endpoints:	Related Hypotheses:

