use changes skin gene expression over time and how these changes may differ based on clinical response to treatment by modeling gene expression before, during (for STS), and after treatment using a linear mixed model based on normalized data that includes a random intercept for each participant and fixed effects for visit, clinical response, disease group, and visit x clinical response group interaction. This model will enable us to examine transcriptional responses to dupilumab treatment between contrasting visits as well as differing transcriptional responses based on clinical response. We will also construct models that predict dupilumab clinical responses as a function of gene expression before treatment. Different clinical response measures will be modeled separately.

Lesional and non-lesional skin, children and adults, and STS and biopsy samples will be analyzed separately, after which expression changes in response to treatment with dupilumab will be compared between skin types, age cohorts, and tissue types.

Determining the changes in cell type-specific gene and protein expression and cellular composition that are associated with dupilumab response and non-response [EO #10]

Adult skin biopsy samples collected from lesional and non-lesional skin will be cryopreserved. Once we have characterized all individuals as being clinical responders ($EASI \leq 7$) or non-responders ($EASI > 7$) to dupilumab, we will select archived lesional/non-lesional sample pairs from participants from each group for single cell proteogenomics (scProteogenomics).

Gene and protein count matrices obtained from Cell Ranger ([Section 9.2](#)) will be separately batch-corrected and normalized, after which gene and protein modalities collected from the same cells will be integrated ([Hao et al, 2021](#)). Dimensionality reduction, cell clustering, and cell type identification based on gene and protein levels will be carried out using a pipeline optimized in the [name] Lab. All samples (both visits, skin types, and responders/non-responders) will be clustered into cell types together.

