To assess changes in cellular composition between visits, between responder and non-responder skin, or between lesional and non-lesional skin, we will explore whether cell types are selectively present or absent within a group. We will calculate cell type composition in each participant sample and then compare individual cell type proportions between visits (for each skin type and response status separately), response statuses (for each visit and skin type separately), and skin types (for each visit and response status separately). Cell type composition will also be compared between groups using multivariate linear mixed models for compositional data. We will also construct models that predict dupilumab clinical response as a function of cell type proportion prior to treatment.

To assess differences in gene/protein expression due to treatment, response status, or skin type, we will identify differentially-expressed genes/proteins between visits (for each skin type separately, controlling for response group), between response groups (for each skin type and visit separately), or between skin types (for each visit separately, controlling for response group) for each cell type separately using a mixed model.

Determining whether AD skin endotypes are associated with topical steroid response [EO #11]

Based on AD endotypes identified using both lesional and non-lesional STS and biopsy samples ([Section 13.4.4.4](#)) (dupilumab-naïve participants only), we will test for an association between skin endotypes and visit, clinical response to topical steroid use, and an interaction between the two. To describe clinical response to topical steroids, we will use in turn the same four targeted and body-wide skin measures of

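### Exploratory Objective 10 asks which cell-level changes go with dupilumab response, but none of its stated per-cell-type tests compares the change between responders and non-responders

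*Protocol*

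**What the plan says.** Protocol section 2.1, Table 2.1.3, gives the objective as "To determine the changes in cell type-specific gene and protein expression and cellular composition that are associated with dupilumab response and non-response". The paired hypothesis is that "Shifts in the cellular composition of skin and cell type-specific gene and protein expression changes underlie clinical response to dupilumab".

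The analysis is in Protocol section 13.4.4 under EO #10:

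- **Cell proportions, each cell type:** the plan is to "compare individual cell type proportions between visits (for each skin type and response status separately), response statuses (for each visit and skin type separately"), and between skin types within each visit and response status.
- **Gene and protein expression, each cell type:** a mixed model is used to identify "differentially-expressed genes/proteins between visits (for each skin type separately, controlling for response group), between response groups (for each skin type and visit separately"), and between skin types at each visit, controlling for response group.
- **Composition as a whole:** "Cell type composition will also be compared between groups using multivariate linear mixed models for compositional data". The model terms are not given and the groups are not defined.
- **Prediction:** dupilumab response is modelled from cell type proportions before treatment.

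The neighbouring EO #9, which puts the same question to bulk expression, specifies "fixed effects for visit, clinical response, disease group, and visit x clinical response group interaction". EO #7, #8, #11 and #12 also name a visit x clinical response interaction. SAP section 2.3 sends all exploratory objectives to a separate Exploratory SAP.

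**The concern.** A change associated with response is a difference between two changes: the pre-to-post change in responders against that in non-responders. Each stated per-cell-type test looks at only part of this.

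The visit test for expression treats response as an adjuster and so returns one average change. The response-group test at a single visit contains whatever gap existed before the first dose plus any difference in change. The proportion tests run within one response status or within one visit, so nothing sets one change formally against the other.

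At stake is attribution. A cell type or gene that shifts equally in everyone on dupilumab, or that already differed before treatment, could be reported as part of the mechanism of response. The remedy is already in the protocol for bulk expression, and no reason is given for its absence from the single-cell tests.

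**Working it through.** **1. What each stated test estimates.** Write R0, R1 for the responder means before and after treatment, and N0, N1 for non-responders. The quantity EO10 needs is D = (R1 − R0) − (N1 − N0).

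| Stated per-cell-type test | What it estimates | Equals D? |
|---|---|---|
| Expression between visits, controlling for response | weighted average of (R1 − R0) and (N1 − N0) | No |
| Expression or proportion between response groups, pre-treatment visit | R0 − N0 | No |
| Expression or proportion between response groups, post-treatment visit | R1 − N1 = (R0 − N0) + D | Only if R0 = N0 |
| Proportion between visits, within one response status | R1 − R0, or N1 − N0, each tested against zero | No |
| Lesional against non-lesional | not a visit or response contrast | No |

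The visit x response coefficient, as in EO9, equals D.

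**2. Inputs for an illustration.** EO10 states no sample size, power or alpha, so there is no EO10 figure to reproduce. Protocol section 13.7.1 gives the adult ceiling:

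- Adults starting dupilumab: 0.50 × 160 + 0.05 × 100 = 85.
- Responders: 0.40 × 85 = 34. Non-responders: 85 − 34 = 51. Both match Table 13.7.1.3.
- With the 20% dropout used in the secondary-objective power tables: about 27 and 41.

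The single-cell assays may be run on a subset (Protocol section 9), so 20 vs 20 and 10 vs 10 are added as assumptions. Also assumed: two-sided 0.05 per test, normal data, one summary value per participant and visit, SD 1 per sample, and pre/post correlation 0.5. The SD of change is then √(2 × (1 − 0.5)) = 1.

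**3. Same true change in both groups, no pre-treatment difference.** If the within-group tests have power p and q, exactly one is significant with probability p(1 − q) + q(1 − p). For 34 vs 51 and a change of 0.4 SD, p = 0.62 and q = 0.80, so 0.62 × 0.20 + 0.80 × 0.38 = 0.43.

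| Groups | Shared change | Exactly one group significant |
|---|---|---|
| 34 vs 51 | 0.3, 0.4, 0.5 SD | 51%, 43%, 23% |
| 27 vs 41 | 0.3, 0.4, 0.5 SD | 49%, 49%, 34% |
| 10 vs 10 | 0.3, 0.4, 0.5 SD | 24%, 33%, 41% |

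The average visit test flags the 0.4 SD shared change in 95% of cases (34 vs 51). That is correct as a statement of change, but it says nothing about response.

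**4. Same change, with a pre-treatment difference carried through.** The probability that the group test at any one visit is significant:

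| Groups | Pre-treatment difference | Flagged |
|---|---|---|
| 34 vs 51 | 0.4, 0.6, 0.8 SD | 43%, 76%, 95% |
| 27 vs 41 | 0.4, 0.6, 0.8 SD | 36%, 67%, 89% |
| 10 vs 10 | 0.4, 0.6, 0.8 SD | 14%, 25%, 40% |

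**5. The interaction test in the same settings.** In simulation (20,000 runs; 34 vs 51 and 27 vs 41) it rejects in about 5%, the nominal rate, with or without a pre-treatment difference.

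**6. What the interaction costs in precision.** With SD of change 1, the average visit effect has SE 1/√85 = 0.108 and the interaction has SE √(1/34 + 1/51) = 0.221, about twice as large. At 80% power and unadjusted 0.05, the detectable difference in change is 2.80 × 0.221 = 0.62 SD. At 10 vs 10 it is 2.80 × √(1/10 + 1/10) = 1.25 SD.

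**The case against.** Several points on the other side have weight.

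- **The planned pre-treatment group test would often expose a baseline difference.** With 20 vs 20 and a 0.8 SD difference it rejects in about 69% of runs. Significance after but not before treatment occurs in about 15%. This stands: the rates in step 4 are not rates of undetected error. It still leaves the reader comparing two p-values, not testing a change.
- **The protocol does not say that significance in one group and not the other will be read as a difference.** True. The percentages in step 3 show how unreliable that reading would be, not something the plan commits to.
- **The multivariate compositional model may contain the interaction.** It may, since its terms are unstated. It would not cover expression, and it is not a test of each cell type.
- **The model using pre-treatment proportions** is a legitimate prediction analysis, but it does not address change.
- **The Exploratory SAP may add the term.** This cannot be excluded. A reader might infer that the whole plan lacks the interaction. The documents support only its absence from the protocol's stated per-cell-type tests.

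A reader might also infer that changes running in opposite directions would be missed because they cancel in the average visit test. The documents do not support that. With changes of ±0.6 SD, 20 vs 20 and no pre-treatment difference, the planned post-treatment group test rejects in about 96% of runs, the same as the interaction. Such changes would be hidden from it only if a pre-treatment difference offset them.

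**Conclusion.** The point holds on the text. EO10's question is a difference in change, and no per-cell-type test stated in Protocol section 13.4.4 estimates it. Followed as written, these tests cannot separate response-specific change from change common to both groups or from a difference present before dupilumab. This is more than missing detail, because specific contrasts are spelled out and they do not answer the objective, while EO9 names the term that does.

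The size can only be illustrated. At the adult ceiling of 34 vs 51, an identical 0.4 SD change gives discordant within-group results in about 43% of cases, and a stable 0.6 SD baseline gap is flagged at one visit in about 76%, against about 5% for the interaction. These figures depend on the assumed sample size, correlation and effect sizes, and the pre-treatment group test would reveal many of the baseline gaps.

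The objective is exploratory, so the primary and secondary conclusions are unaffected. EO9 still provides a response-specific test of change in bulk biopsy expression, though not by cell type. Confidence is high that the protocol text omits the term, and lower for the plan as a whole because the Exploratory SAP was not available.

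**What to change.** In Protocol section 13.4.4, EO #10, and in the Exploratory SAP:

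1. For each cell type and skin type, fit visit, response and visit x response with a participant random effect, both for gene and protein expression and for individual cell type proportions.
2. Name the visit x response term as the EO10 test of response-associated change.
3. State the terms of the multivariate compositional model and include the same interaction.
4. Keep the present within-visit, within-status and average-visit contrasts as descriptive follow-up, and keep the pre-treatment prediction model as a separate question.
5. Check that the Exploratory SAP carries the same specification.

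The cost is a change of wording and one model term. EO10 already draws on samples from both visits and both response groups, so no new samples are needed. The interaction's standard error is about twice that of the average visit effect (0.221 against 0.108 SD at 34 vs 51), and a small single-cell subset would detect only large differences in change. Those wider intervals reflect the information the data hold on this question.

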	(dupilumab-naïve participants only) 18. Non-lesional and lesional skin biopsy endotypes determined in exploratory objective 4 (dupilumab-naïve adults only)	determined by skin endotype status.
12. To determine whether AD skin endotypes are associated with dupilumab response	19. Non-lesional and lesional skin tape endotypes determined in exploratory objective 4 (dupilumab-naïve participants only) 20. Non-lesional and lesional skin biopsy endotypes determined in exploratory objective 4 (dupilumab-naïve adults only)	12. The clinical response to dupilumab treatment will be determined by skin endotype status.
13. To determine whether cell type-specific gene and protein expression and cellular composition differ among AD skin endotypes	21. Single cell non-lesional and lesional skin biopsy transcriptome and proteome (adults only)	13. Shifts in the cellular composition of skin and cell type-specific gene and protein expression changes underlie skin endotypes.
14. To determine longitudinal changes in skin (skin tape) gene expression across standard-of-care treatment (all timepoints) in the study outcome groups: (1) topical steroid responders, (2) dupilumab responders, (3) dupilumab non-responders, (4) non-AD, and (5) long-term dupilumab participants	22. Non-lesional and lesional skin tape transcriptome	14. The clinical response to protocol's standard-of-care treatment among different AD participants will be associated with distinct transcriptional trajectories generated across these standard-of-care treatments.
15. To determine whether genetic variation that regulates skin gene expression is associated with AD disease	23. Non-lesional and lesional skin tape and skin biopsy transcriptome 24. Genome-wide genotypes from blood samples	15. Genetic variation drives particular AD skin endotypes.
16. To determine the proteomic profiles of AD lesional and non-lesional skin endotypes	25. Non-lesional and lesional skin tape proteome	16. AD skin endotypes exhibit distinct epidermal protein profiles.
17. To determine the lipidomic and metabolomic properties of AD lesional and non-lesional skin endotypes	26. Non-lesional and lesional skin tape lipidome and metabolome	17. AD skin endotypes exhibit distinct lipid and metabolome profiles.

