At Day 140, topical steroid responders will come in for a 19 Week Steroid Assessment when they will discontinue applying triamcinolone/hydrocortisone to active lesions on the target skin area and begin to apply Vanicream™ Moisturizing Cream at least twice daily to target skin. Triamcinolone/hydrocortisone may continue to be used on active lesions on non-target skin. Participants will return for an End of Study Assessment at Day 168.

Topical Steroid Non-responders

Topical steroid non-responders will discontinue application of triamcinolone to the target area and continue to refrain from applying Vanicream™ Moisturizing Cream to the target area, unless required at any point as a rescue treatment at the discretion of the investigator. They may apply triamcinolone/hydrocortisone to active lesions on non-target areas as needed. Topical steroid non-responders beginning treatment with dupilumab will initially receive a loading dose of two subcutaneous injections at the Dupilumab Initiation Visit within 3 days of the qualifying EASI score (EASI > 7 beginning at the 4 Week Steroid Assessment through the 12 Week Steroid Assessment). They will be provided with additional doses to take home to self-administer by subcutaneous injection according to their dose schedule outlined in [Section 6.1.3](#). Topical steroid non-responders will return for up to three additional scheduled visits prior to their End of Study Visit: an Optional Dupilumab Assessment, 4 Week Dupilumab Assessment, and a 15 Week Dupilumab Assessment.

If symptoms worsen at any time between planned study visits, participants can be scheduled for an Unscheduled Visit. If disease becomes uncontrolled in a participant on dupilumab despite treatment with rescue medications ([Section 7.4](#)), per investigator judgment, the participant will complete an Early Termination Visit and will be classified as having experienced a treatment failure.

By the 15 Week Dupilumab Assessment, participants will have concluded treatment with dupilumab. During this visit, the topical steroid non-responders will be instructed to begin to apply Vanicream™ Moisturizing Cream at least twice daily to target skin. Participants will return for an End of Study Assessment approximately 133 days after Dupilumab Initiation.

Figure 3.1.1 Dupilumab-naïve AD Participant Flow Chart

[figure not shown]
[‡]Screening and Baseline Visits may occur on the same day

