8.6 Dupilumab Initiation Visit

DNAD participants classified as Topical Steroid Non-Responders ($EASI$ score > 7 any time from the 4 Week Steroid Assessment through the 12 Week Steroid Assessment) will begin treatment with dupilumab.

The Dupilumab Initiation Visit will ideally be completed on the same day as the study visit at which the qualifying $EASI$ score was obtained (e.g., Day 35 if the score was elevated at the 4 Week Steroid Assessment) and must be completed within 3 days of a qualifying $EASI$ score (see [Section 8.13](#) for Visit Windows). When dupilumab initiation is completed within window ([Section 8.13](#)), activities that overlap will not be repeated. The following procedures and assessments will be conducted at the Dupilumab Initiation Visit:

- Interim medical history
- Physical examination (abbreviated at investigator discretion)
- Assessments of AD severity ($EASI$, IGA, SCORAD, PP-NRS, TAA, and targeted $EASI$)
- Allergic disease questionnaires
- Confirm pregnancy status (if applicable), including performing a urine pregnancy test
- Assessment of concomitant medications
- Vital signs, including temperature, blood pressure, heart rate, and respiratory rate; and growth parameters, including height and weight
- Blood collection; approximately 20 mL for serum/plasma biomarkers and approximately 2 mL for a CBC with differential

- Photographs will be taken of the measured lesional and non-lesional sites for collection of skin swabs, tape strips, and biopsies, as applicable
- Skin swab collection; up to 6 swabs
- STS collection; up to 40 STS
- Two required 2.5 mm skin biopsies for molecular assays, adults only
- Up to two optional 2.5 mm skin biopsies for molecular assays, adults only
- Distribute triamcinolone and hydrocortisone, as applicable
- Administer and distribute dupilumab
- Assessment of AEs

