clinical response described in [Section 13.4.4.7](#). Specifically, we will use a logistic regression model appropriate for repeated measures to predict endotype status (high or low) as a function of visit, clinical response, disease group, and visit x clinical response interaction. The interaction term enables testing for whether the relationship between visit and endotype differs based on clinical response. We will also construct models that predict steroid clinical response as a function of endotype status before treatment. This will enable us to investigate any associations between clinical response to treatment and baseline endotype. Separate analyses will be performed for children and adults, for each endotype (stratified by lesional and non-lesional skin), and for STS and biopsy samples.

Determining whether AD skin endotypes are associated with dupilumab response [EO #12]

Based on AD endotypes identified using both lesional and non-lesional STS and biopsy samples ([Section 13.4.4.4](#)) (dupilumab-naïve topical steroid non-responders only), we will test for an association between skin endotypes and visit, clinical response to dupilumab (using in turn the two body-wide measures described in [Section 13.4.4.7](#)), and an interaction between the two. Specifically, we will use a logistic regression model appropriate for repeated measures to predict endotype status (high or low) as a function of visit, clinical response, disease group, and visit x clinical response interaction. This model will enable us to examine relationships between endotype status and visit as well as determine how these relationships change with clinical response. We will also construct models that predict dupilumab clinical response as a function of endotype status before treatment. Separate analyses will be performed for children and adults, for each endotype (stratified by lesional and non-lesional skin), and for STS and biopsy samples.

Determining whether cell type-specific gene and protein expression and cellular composition differ among AD skin endotypes [EO #13]

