						Optional Steroid Assessment	12 Week Steroid Assessment ⁵	19 Week Steroid Assessment	End of Study Assessment	Early Termination ²	Early Withdrawal/Termination Follow-Up ³	Unscheduled Visit ⁴
Target Day ¹⁷		-7	0	7	35	40	91	140	168			
Study Procedures/Evaluations												
Recruitment	X											
Informed Consent		X										
Demographics		X										
Adverse Events		X	X	X	X	X	X	X	X	X	X	X
Concomitant Medications		X	X	X	X	X	X	X	X	X	X	X
Pregnancy Status		X	X	X	X	X	X	X	X	X	X	X
Pregnancy Test ⁶			X	X								
Medical History		X	X ⁷	X ⁷	X ⁷	X ⁷	X ⁷	X ⁷	X ⁷	X ⁷		X ⁷
Physical Exam			X	X ⁷	X ⁷	X ⁷	X ⁷	X ⁷	X ⁷	X ⁷		X ⁷
Vital Signs/Growth Parameters ⁸			X	X	X	X	X	X	X	X		X
Allergic Disease Questionnaires			X	X	X		X	X	X	X		X
AD Severity Assessments												
Eczema Area and Severity Index (EASI)			X	X	X	X	X	X	X	X		X
Scoring Atopic Dermatitis (SCORAD)			X	X	X	X	X	X	X	X		X
Investigator Global Assessment (IGA)			X	X	X	X	X	X	X	X		X
Peak Pruritus Numerical Rating Scale (PP-NRS)			X	X	X	X	X	X	X	X		X
Skin Target Area Assessment (TAA)			X	X	X	X	X	X	X	X		X
Nottingham Eczema Severity Score (NESS)			X						X	X		X
Blood Sample Collection												
CBC w/differential				X	X			X	X	X		X ⁹
Genetics ¹⁰				X								X
Serum/Plasma Biomarkers				X	X			X	X	X		X
Skin Sampling Location Photographs			X	X	X	X	X	X	X	X		X
Skin Swab Collection												
S. aureus Abundance (Les, NL)			X	X	X	X	X	X	X	X		X
Microbiome 16S rRNA analysis (Les, NL)			X	X	X	X	X	X	X	X		X
Metagenomics (Les, NL)			X	X	X	X	X	X	X	X		X
Microbiome Functional Assessment (Les, NL)			X	X	X	X	X	X	X	X		X

Study Visit	Recruitment	Screening	Baseline Assessment	Steroid Initiation	4 Week Steroid Assessment ¹	Topical Steroid Responders						
						Optional Steroid Assessment	12 Week Steroid Assessment ⁵	19 Week Steroid Assessment	End of Study Assessment	Early Termination ²	Early Withdrawal/Termination Follow-Up ³	Unscheduled Visit ⁴
Skin Tape Stripping												
Transcriptomics (Les, NL)			X	X	X		X	X	X	X		X
Lipidomics (Les, NL)			X	X	X		X	X	X	X		X
Proteomics (Les, NL)			X	X	X		X	X	X	X		X
Skin Biopsy¹¹												
Optional Biopsies (Les, NL)				X					X	X		X ¹²
Treatment Distribution												
Vanicream™ Moisturizing Cream			X ¹³					X ¹⁴				
Triamcinolone / Hydrocortisone				X ¹⁵	X ¹⁶		X ¹⁶	X ¹⁶				

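### EO #11 tests a visit-by-steroid-response interaction in biopsy endotypes, but only steroid non-responders have a scheduled biopsy at the end of steroid treatment

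*Protocol*

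**What the plan says.** The EO #11 text in Protocol Section 13.4.4 states that "we will test for an association between skin endotypes and visit, clinical response to topical steroid use, and an interaction between the two". The model is a repeated-measures logistic regression to "predict endotype status (high or low) as a function of visit, clinical response, disease group, and visit x clinical response interaction". The biopsy strand is explicit: "Separate analyses will be performed for children and adults, for each endotype (stratified by lesional and non-lesional skin), and for STS and biopsy samples". Section 2.1 lists the matching endpoint (no. 18) as "Non-lesional and lesional skin biopsy endotypes determined in exploratory objective 4 (dupilumab-naïve adults only"). A second EO #11 model predicts steroid response from the endotype before treatment.

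Response is measured in four ways, defined under EO #7: shift in TAA, shift in targeted EASI, shift in body-wide EASI, and a body-wide EASI cut at 7.

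The biopsy schedule is set elsewhere:
- **Day 7 (Section 8.4).** Biopsies are optional for adults in both response groups.
- **4 Week Steroid Assessment (Section 8.5).** Swabs and tape strips are listed; no biopsy is.
- **Appendix A, dupilumab-naïve table.** The row "Optional Biopsies (Les, NL") is marked at Steroid Initiation, End of Study, Early Termination and Unscheduled. It is blank at the 4, 12 and 19 Week Steroid Assessments.
- **Dupilumab Initiation (Section 8.6).** The list has "Two required 2.5 mm skin biopsies for molecular assays, adults only". Only participants with EASI > 7 reach this visit, and it falls on the day of the qualifying score or within 3 days of it.

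On steroid exposure in responders, Section 3.1.1 stops triamcinolone on non-lesional target skin after the 4 Week visit. At Day 140 "they will discontinue applying triamcinolone/hydrocortisone to active lesions on the target skin area" and start moisturizer there.

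**The concern.** A visit-by-response interaction asks whether the endotype changes differently over steroid treatment in responders and non-responders. That needs a biopsy in both groups before steroid and at a comparable point on or at the end of steroid. Both groups can have the first. Only non-responders have a scheduled second one.

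Any biopsy interaction between the two groups therefore mixes steroid response with something else that the schedule ties to it. A difference produced by the sampling plan could then be read as a difference in steroid response.

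**Working it through.** **1. Group sizes (Section 13.7.1).** Adult non-responders: 160 × 0.50 + 100 × 0.05 = 85, as stated. Adult responders: 260 − 85 = 175, as in Table 13.7.1.3. Scheduled end-of-steroid biopsies are therefore available from up to 85 non-responders and 0 of 175 responders.

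**2. Timing (Sections 3.1.1 and 8.13).**

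| | Non-responders, Dupilumab Initiation | Responders, End of Study |
|---|---|---|
| Target day | 35 to 91 | 168 |
| Days after Day 7 | 28 to 84 | 168 − 7 = 161 |
| Target lesions off steroid | 0 to 3 days after the qualifying EASI | 168 − 140 = 28 days |
| Target non-lesional skin off steroid | near 0 if initiated at Day 35; up to 91 − 35 = 56 days in late crossovers | 168 − 35 = 133 days |

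With visit windows, the non-responder biopsy falls from Day 32 to Day 94 + 3 = 97, that is 25 to 90 days after Day 7.

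**3. What each visit coding can estimate, dichotomous measure.** The scheduled biopsy cells are Day 7 and End of Study for responders, and Day 7, Dupilumab Initiation and End of Study for non-responders. The non-responders' 15 Week Dupilumab biopsy is left out; it would add one more level with no responder cell.
- *Separate visit levels.* Intercept, two visit terms, response and two interactions make 6 parameters. Five filled cells give rank 5. The end-of-steroid interaction is not estimable.
- *Pooled pre/post* (post is Dupilumab Initiation for non-responders and Day 168 for responders). There are four cells. Adding an on-steroid indicator to intercept, visit, response and interaction gives 5 columns and rank 4. The interaction is aliased with on/off steroid, and with elapsed time as well.
- *Day 7 vs End of Study in both groups.* The interaction is estimable, but by then the non-responders have been treated with dupilumab and the responders have not.

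**4. Continuous measures.** These vary within non-responders, so an interaction between Day 7 and Dupilumab Initiation can be fitted there. It describes only participants selected for EASI > 7.

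**5. Tape, for comparison.** All dupilumab-naïve participants have tape scheduled at Day 7 and Day 35. The model with intercept, visit, response and interaction has 4 parameters and rank 4.

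**6. Illustration of the pooled coding.** These assumptions are not in the documents: the same true steroid odds ratio (OR) in both groups, a fraction ρ of the effect lost by Day 168 in responders, 50% endotype-high at Day 7, independent samples, equal biopsy uptake in every cell, and two-sided alpha 0.05. The spurious log interaction is (1 − ρ) ln OR − ln OR = −ρ ln OR, so the spurious ratio of odds ratios is OR^(−ρ).
- OR 0.5: 1.41 at ρ = 0.5 and 2.0 at ρ = 1.
- OR 0.25: 2.0 at ρ = 0.5 and 4.0 at ρ = 1.

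The Wald variance is the sum of 1/[n p(1 − p)] over the four cells. For OR 0.5, ρ = 1 and full uptake, it is 2/(175 × 0.25) + 1/(85 × 0.25) + 1/(85 × 0.222) = 0.146. The standard error is 0.382, z = 0.693/0.382 = 1.82, and the chance of a significant result is 0.44. Over OR 0.5 to 0.25, ρ 0.25 to 1 and uptake 25% to 100%, that chance runs from 0.06 to 0.92.

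**The case against.** The strongest reply is that the plan fixes no biopsy visits for EO #11. Section 2.1 defers exploratory timepoints to the SAP, and SAP Section 2.3 sends them to a separate Exploratory SAP that is not among the documents. This limits what can be concluded. A reader might infer that the plan, followed as written, will report a sampling artefact as a steroid-response effect. The documents do not support that. The artefact arises under pooled pre/post coding, which nowhere appears in the text, and with separate visit levels there would be no estimate to report. The reply does not remove the problem, because no choice among scheduled visits supplies a responder biopsy at the end of steroid treatment.

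Other points stand in part:
- Early Termination and Unscheduled visits allow biopsies, so a few responders could contribute an on-steroid sample. These are unplanned. Appendix A bars biopsies at unscheduled flare visits, and Early Termination would include late steroid failures.
- It is tempting to call all 85 non-responder biopsies on-steroid. For non-lesional target skin in late crossovers that is too strong, since steroid may have stopped there after Day 35.
- Some biopsy analyses survive: visit contrasts within a response group, and continuous-measure models within the selected non-responders.
- The EO #11 hypothesis, that endotype determines steroid response, is addressed most directly by the Day 7 predictive model, for which both groups share the same biopsy visit.

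**Conclusion.** The point holds for the biopsy visit-by-response interaction in EO #11. For the dichotomous measure, no set of scheduled visits isolates steroid response. For the continuous measures, the end-of-steroid interaction is confined to participants with EASI > 7. The size is structural: up to 85 planned adults against 0 of 175 with a scheduled end-of-steroid biopsy. The odds ratios and error rates above only illustrate one coding and are not forecasts.

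This rests on the Appendix A marks, the planned group sizes, and the protocol's rule that EASI > 7 at any time through the 12 Week visit makes a participant a non-responder.

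A reader might extend this to EO #11 as a whole, or to biopsy endotypes in general. That would be wrong: the tape strand and the Day 7 predictive model are sound on this point. The matter is exploratory and minor, and the primary and secondary objectives are untouched.

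**What to change.** In Protocol Section 13.4.4 (EO #11) and the Exploratory SAP:
1. Restrict the visit-by-response interaction test to tape samples at Day 7 and the 4 Week Steroid Assessment (Day 35). Naming both visits matters, because the 12 and 19 Week steroid tape samples are on the responder schedule only. EO #8, the gene-expression counterpart, already uses tape alone.
2. Use biopsy endotypes for the Day 7 model that predicts steroid response.
3. Report any biopsy visit contrast within response group only, as descriptive, and do not attribute differences between groups to steroid response.

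The cost is a text change and the loss of one exploratory biopsy interaction test. No biopsy, visit or treatment rule changes.
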